7.2.5 Shoulder Pain and Disability Index (SPADI) - Parts B and C only

SPADI will only be assessed on the patients whose tumor is in shoulders.

This measurement was added in after the protocol amendment v03, hence the analysis plan below only applies to the data collected afterwards.

The Shoulder Pain and Disability Index (SPADI) is a self-administered questionnaire that consists of two dimensions, one for pain and the other for functional activities. The pain dimension consists of five questions regarding the severity of an individual's pain. Functional activities are assessed with eight questions designed to measure the degree of difficulty an individual has with various activities of daily living that require upper-extremity use.

Total pain score: sum of 5 questions / 50 x 100%

(Note: If a person does not answer all questions divided by the total possible score, e.g. if 1 question missed divide by 40)

Total disability score: sum of 8 questions / 80 x 100 %

(Note: If a person does not answer all questions divided by the total possible score, e.g. if 1 question missed divide by 70)

Total Spadi score: sum of all 13 questions/ 130 x 100 %

(Note: If a person does not answer all questions divided by the total possible score, e.g. if 1 question missed divide by 120)

Part B

Summary statistics and graphical displays of overall SPADI score and absolute change from baseline in SPADI score will be provided with MCS110 arms pooled. All SPADI data will be listed by treatment group.

Part C

Summary statistics and graphical displays of overall SPADI score and absolute change from baseline in SPADI score will be provided by treatment group. All SPADI data will be listed by treatment group.

7.2.6 Joint Pain measured on a Visual Analogue Scale (VAS) - Part B* and C only

During the study, patient's pain will be assessed with a 100 mm visual analog scale (VAS).

The pain VAS will be completed by the patient. The patient will be asked to place a line perpendicular to the VAS line at the point that represents his/her pain intensity. Using a ruler,

the score is determined by measuring the distance (mm) on the 10-cm line between the “no pain” anchor and the patient’s mark, providing a score from 0-100.

Part B

Summary statistics and graphical displays of overall VAS pain scores and absolute change from baseline mean(\pm SE) will be provided over time with MCS110 arms pooled. All VAS data will be listed by treatment group.

Part C

Summary statistics and graphical displays of overall VAS pain scores and absolute change from baseline mean(\pm SE) will be provided over time by treatment group. All VAS data will be listed by treatment group.

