3.2.3.1 Part B

The first dose of the multiple dose Part B will continue to be placebo controlled and double blind to complete the original study plan and analyze the reduction in tumor volume and symptoms after single dose and four weeks of treatment. Tumor growth is expected to be minimal within 4 weeks (<10%) and this has been confirmed so far in the one placebo treated patient with a tumor volume change of -2 %. As in Part A in Part B patients are randomized in a 2:1 ratio of active versus placebo to keep the number of placebo treated patients as low

as possible, but still allow assessment of active treated versus placebo treated patients. Patients will only receive a single dose of placebo and then will be shifted to active treatment. After the first dose, the multiple dose Part B will then continue as an open label study to allow all patients to benefit from 4 doses of MCS110 treatment. It is recognized, that subjective responses will be impacted by open label treatment, but 1) the primary outcome is longer-term tumor shrinkage, which is based on an objective measure and thus should not be affected by open label and 2) the study will have the first month's treatment blinded and the main clinical response seems to happen quite quickly (based on the first 5 patients), so this will still be an evaluable secondary endpoint at day 28.

Day 1 treatment will be maintained double-blind until week 12 when the fourth dose will be administered. Depending on the treatment received for the first dose, un-blinding will allow Day 1 placebo patients to receive 3 additional doses of MCS110 and Day 1 MCS110 patients to receive 2 additional doses of MCS110 up to a total of 6 consecutive dose administrations of MCS110.

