9.5 Analysis of secondary variables

The first 4 weeks data from Part A, Part B, and Part C will be pooled together for analyses. In addition, data in Part B will be analyzed by treatment groups; we may also pool treatment groups by matching the 1st dose of MCS110 in treatment group 1 to the 2nd dose (1st of MCS110) in treatment group 2.

Part C analyses of secondary variables will be done by treatment group. We may also pool treatment groups across Parts B and C to analyze secondary variables.

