The same model as above will also be applied to compare the efficacy of the 3 mg/kg and 5 mg/kg to the 10 mg/kg dose (instead of Placebo).

Part B and C (referenced as Part B* hereafter)

Part B includes all data from multiple dosing Parts. In Part B, treatment group 1 = MCS110 throughout the trial, treatment group 2 = Placebo for the first dose and MCS110 from the second dose. In Part C, treatment arm 1 = MCS110 3 mg/kg, treatment arm 2 = MCS110 5 mg/kg, treatment arm 3 = MCS110 10 mg/kg, for patients in treatment arms 1 and 2 that switch to 10 mg/kg after 3 doses, they will be included in their original treatment group for the first 3 doses and will added in a separate group after that (4= MCS110 3 mg/kg for 3 doses and 10 mg/kg afterwards and 5= MCS110 5 mg/kg for 3 doses and 10 mg/kg afterwards), no re-calculation of baseline will occur for the people who change treatments.

Tumor volumes will be listed at each MRI assessment timepoint till the end of the study by treatment groups.

Part B*: MCS110 data only, by including data starting from the 1st dose of MCS110 in all treatment groups of Parts B and C. More specifically, for Part B treatment group 2, the measurement right before patients receiving the first dose of MCS110 (2nd dose from screening) will be treated as the new baseline and assessment time-points will be adjusted accordingly. Summary statistics of the consolidated tumor volume for the raw values, percent change and absolute change from baseline.

Arithmetic mean (+/-) SE on percent change from baseline vs time plot will be produced for Part B*. Waterfall plot of the maximum reduction until 8 Weeks after last dose will be produced in regards of number of doses received.

Overall Time to complete tumor ablation will be summarised up to the primary endpoint (8 weeks after the last MCS110 dose), along with a summary of overall time to $\geq 50\%$, and $\geq 80\%$ ablation. The number and frequency of patients reaching each level will also be included in the summary.

Overall Time to complete ablation is the time (in weeks) - from first MCS110 dose to the first time when there is no tumor detected. Overall time to $\geq 50\%$, and $\geq 80\%$ ablation is the time from first MCS110 dose to reach maximum ablation of [50%, 80%) and [80%, complete) respectively.

Part C

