A total score has not been validated and is not recommended.

Part B

Summary statistics presenting each of KOOS sub scores and absolute change from baseline in each KOOS sub score will be provided with MCS110 arms pooled (Part B*). Panelwise graphs per sub-score will be used, where mean (+/-SE) will be plotted over time with MCS110 arms pooled (Part B*). All KOOS data will be listed by treatment group (defined in Part B).

Part C

Summary statistics presenting each of KOOS sub scores and absolute change from baseline in each KOOS sub score will be provided. Panelwise graphs per sub-score will be used, where mean (+/-SE) will be plotted over time by treatment group. All KOOS data will be listed by treatment group.

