7.2.4 Patient Rated Elbow Evaluation (PREE) – Parts B and C only

PREE will only be assessed on patients whose tumor is in elbows.

This measurement was added in after the protocol amendment v03, hence the analysis plan below only applies to the data collected afterwards.

The PREE is a 20-item questionnaire designed to measure elbow pain and disability in activities of daily living. The PREE allows patients to rate their levels of elbow pain and disability from 0 to 10, and consists of 2 subscales:

1) PAIN subscale (0 = no pain, 10 = worst ever)

Pain - 5 items

2) FUNCTION subscale (0 = no difficulty, 10 = unable to do)

Specific activities - 11 items

Usual activities - 4 items

In addition to the individual subscale scores, a total score out of 100 can be computed by equally weighting the PAIN subscale score (sum of five items) and the FUNCTION subscale score (sum of fifteen items, divided by 3).

Computing the Subscales

Pain Score = Sum of the 5 pain items (out of 50). Best Score = 0, Worst Score = 50

Function Score = Sum of the 15 function items, Divided by 3 (out of 50) Best Score = 0, Worst Score = 50

Computing the Total Score

Total Score = Sum of pain + function scores. Best Score = 0, Worst Score = 100

If there is an item missing, the item will be replaced with the mean score of the subscale.

Part B

Summary statistics and graphical displays of total PREE score and absolute change from baseline in PREE score will be provided with MCS110 arms pooled (Part B*). All PREE data will be listed by treatment group (Part B).

Part C

Summary statistics and graphical displays of total PREE score and absolute change from baseline in PREE score will be provided by treatment group. All PREE data will be listed by treatment group.

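### For Part B, the SAP summarises pain and joint-function scores only on pooled MCS110 data from the first MCS110 dose, leaving the blinded placebo month to listings

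*SAP*

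**What the plan says.** Joint pain and functional recovery, the latter including KOOS, SPADI and PREE, are secondary objectives of Part B (Protocol 2.5).

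Protocol 3.2.3.1 accepts that open-label treatment will influence subjective responses. Part of its answer is that the first month is blinded and the main response appears early, so that this will "still be an evaluable secondary endpoint at day 28". Protocol 9.5 then says that "data in Part B will be analyzed by treatment groups". Matching groups on their first MCS110 dose is something the team may also do.

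The SAP sections for these instruments specify only the pooled version for Part B:

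- KOOS (SAP 7.2.3): "absolute change from baseline in each KOOS sub score will be provided with MCS110 arms pooled (Part B", where the label, cut short in the quotation, is Part B\*.
- PREE (SAP 7.2.4): "absolute change from baseline in PREE score will be provided with MCS110 arms pooled (Part B", with the same label.
- VAS (SAP 7.2.6): summaries and graphs "will be provided over time with MCS110 arms pooled", under the heading "7.2.6 Joint Pain measured on a Visual Analogue Scale (VAS) - Part B* and C only".
- SPADI (SAP 7.2.5): the same pooled wording, but without the Part B\* label.

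SAP 7.1 defines Part B\* as "MCS110 data only, by including data starting from the 1st dose of MCS110 in all treatment groups" of Parts B and C. For patients given placebo first, the measurement just before their first MCS110 dose becomes the new baseline and the time points are shifted. For all four instruments, the by-group Part B output is a listing.

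**The concern.** Part B compares MCS110 with placebo under blinding for four weeks. After that everyone knows they are receiving active drug. A pain or function score can improve over that later period through expectation or regression to the mean as well as through the drug. The blinded month is the part of the design that can separate these.

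The Part B\* rule discards that month from the summaries and uses its last value as the pre-treatment baseline for the placebo-first patients. What is reported for Part B on these scores is then a before-after change without a placebo reference. A reader of the study report would have to rebuild the comparison from listings. The SAP also keeps the analysis that the protocol made optional and leaves out the one that the protocol stated as planned.

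**Working it through.** No stated figure is in dispute, so the check is mainly one of text against text, followed by the precision of the missing comparison.

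**1. Is the placebo month excluded from the summaries?** For KOOS and PREE this is explicit, through the Part B\* label and its definition. For VAS it follows from the section heading. For SPADI it is inferred from identical wording. None of the four sections has a weeks 1 to 4 output (the SAP's Part A\* pool), although Protocol 9.5 also says that the first four weeks of Parts A, B and C will be pooled for secondary analyses. Range of motion (SAP 7.2.2) and EQ5D (SAP 7.3.3.3) do have weeks 1 to 4 outputs.

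**2. Could another part of the trial supply a placebo comparison?** The protocol synopsis restricts the joint questionnaires and pain VAS to Parts B and C, and Part C has no placebo (Protocol 3.5.4.3). The first four weeks of Part B are therefore the only placebo-controlled period with these instruments.

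**3. Do the data exist?** The Part B assessment schedule places VAS and the joint questionnaires at screening, baseline, week 2 and before dosing at week 4. All of these precede the first open-label dose. Protocol 6.4.5 also describes a daily home pain diary for 14 days after the first treatment. For a placebo-first patient those entries would fall wholly inside the excluded month.

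**4. How many patients?** Protocol Section 1 (Study CMCS110X2201) gives 11 patients in Part B. Protocol 9.4.4 and SAP 7.1.2 give 3 placebo patients in Part B, so 11 − 3 = 8 started on MCS110. As a consistency check on the pooled counts in those same sections: 5 active patients in Part A (Protocol 3.5.1), 11 in Part B and 3 in the Part C 10 mg/kg arm (Protocol 5.2.3) give 5 + 11 + 3 = 19 on 10 mg/kg. Placebo is 2 + 3 = 5. Both match.

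**5. Precision for VAS.** The documents give no SD for the VAS change, so results are in SD units and then for an assumed SD of 20 to 25 mm, at two-sided 5%.

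- Standard error factor: √(1/8 + 1/3) = √0.4583 = 0.677.
- Half-width of the 95% interval: t(0.975, 9 df) × 0.677 × SD = 2.262 × 0.677 × SD = 1.53 SD.
- At SD 20 mm: 1.53 × 20 ≈ 31 mm. At SD 25 mm: 1.53 × 25 ≈ 38 mm.
- Power for a true difference of 1 SD, from the noncentral t distribution with noncentrality 1/0.677 = 1.48: about 26%. The difference detectable with 80% power is about 2.1 SD.
- Protocol 9.13 anticipated about 12 patients in Part B. With 8 versus 4 the half-width is 1.36 SD, or about 27 to 34 mm.

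These counts apply to VAS only. KOOS, SPADI and PREE are each limited to one joint, and other tumour locations get no joint questionnaire (Protocol 6.4.4). The SAP also limits their analysis to data collected after amendment v03. The documents do not give numbers per joint.

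**The case against.** Several points on the other side are sound.

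- **The data are not lost.** All four instruments are listed by treatment group. With about three placebo patients, a listing shows every placebo-month value. What is missing is a summary, plot or contrast.
- **Protocol 3.2.3.1 names no instrument.** The text speaks of the main clinical response in the first five patients. A reader might infer a commitment to compare VAS or KOOS between arms at day 28, but that is not written there. The sentence does answer a concern about subjective responses. The firmer basis is Protocol 9.5.
- **Pooling is allowed.** Protocol 9.4.2 lets the re-basing apply across Section 9 if needed. It is offered as an addition, however, and does not replace the by-group analysis.
- **Other controlled or early data remain.** A reader might infer that every pain and function result in the trial is an uncontrolled before-after change. The documents do not support that. Part C scores are summarised by treatment group in a study part that is randomised and double-blind for dose, subject to SAP 7.1's separate grouping of patients who switch dose. Range of motion and EQ5D have weeks 1 to 4 outputs, though neither section states a formal contrast with placebo.
- **The yield is small.** Part B is exploratory, Protocol 9.14 plans no power for secondary variables, and the interval is wide. By-arm PREE or SPADI tables could have no placebo patient at all.
- **Parts of the SAP are redacted or not visible.** An output placed there cannot be ruled out, but the sections governing these instruments can be read.

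These points narrow the scope and the weight. They do not explain why the by-group summary stated in the protocol is missing for these scores.

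**Conclusion.** The point holds in a limited form. For KOOS, PREE and VAS, and probably SPADI, the SAP omits the by-treatment-group Part B analysis stated in Protocol 9.5. It reports only pooled MCS110 data re-based to the first MCS110 dose. The summarised Part B changes in these scores are therefore not placebo-controlled, although blinded placebo data were scheduled for collection and will be listed.

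The consequence is confined to how these secondary outcomes are interpreted. The primary endpoint and the Part C dose decisions are untouched. Restoring the comparison removes an avoidable source of bias from the description but does not give a precise estimate. The size rests on about 8 versus 3 patients for VAS, all with usable scores, and on an assumed SD. The joint questionnaires will have fewer.

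**What to change.** In SAP 7.2.6, add a Part B summary and plot of VAS at weeks 2 and 4, as change from the pre-Day 1 baseline by randomised Day 1 treatment. Include the 14-day pain diary where it was collected. In SAP 7.2.3, do the same for the KOOS subscales. In SAP 7.2.4 and 7.2.5, show PREE and SPADI by arm only if both arms include patients with that joint affected. State in 7.2.5 whether the Part B\* re-basing applies.

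Label the new outputs as the blinded placebo-controlled comparison, descriptive only. Keep the pooled Part B\* outputs and label them as the uncontrolled longer-term description.

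The cost is a few tables and figures and some SAP wording, with no new visits, patients or data collection. The drawback is imprecision: with about three placebo patients the results should be read as individual values with a rough contrast, and no test should be attached.

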7.2.7 Time to surgery – listed for Parts B and C only

Patients with their time to surgery will be listed by Part and treatment groups as defined in Section 7.1. Time to surgery is the time from first dose to surgery.

7.2.8 Time to relapse – listed by Part

Patients who experience recurring PVNS tumor / tumor growth of residual tumor and their time, location, etc. to relapse /re-growth will be listed by Part and treatment group.

Corporate Confidential Information

Corporate Confidential Information

7.3.3 Bone Mineral Density by DXA- Parts B and C only

For exploratory purpose in Parts B and C summary statistics and graphical displays for the change from baseline DXA will be provided by Part. In addition, the data will be listed by Part showing the baseline, raw value and absolute change from baseline. All DXA data will be listed by Part.

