patients with a history of renal diseases are excluded. Serum creatinine will be monitored to follow kidney function. Alveolar macrophages may be affected as well – although this was not observed in preclinical toxicology studies - and consequently patients with a history of lung disease are excluded from recruitment. Furthermore, monocyte derived cells are found as microglial cells in the brain as well as within the bone marrow, spleen, lymph nodes, skin and serosal surfaces. Patients will be closely monitored with physical examination to detect changes.

 Risks associated with MCS110 induced reduction in osteoclasts are hypocalcemia and hypophosphatemia and changes in bone turnover/homeostasis: Corporate Confidential Information

Patients who are enrolled in this study must have normal serum ionized calcium and serum phosphate at screening and baseline and will be closely monitored for the calcium levels at regular intervals throughout the study. Patients who develop hypocalcemia or hypophosphatemia will receive immediate treatment and will be monitored at least on a weekly basis until they return to the normal range. Changes in bone turnover and bone homeostasis will be closely monitored. Corporate Confidential Information

• Risk of developing swelling:

Corporate Confidential Information

Two subjects in the highest dose group used in this study did develop non-pitting periorbital swelling; however, the overall conclusion of the abstract was that the therapy was tolerated well suggesting that Pfizer observed reversibility Periorbital swelling was observed in 1 of 5 patients in Part A, in 6 of 11 MCS110 treated patients in part B and in 15/18 patients in Part C. In all patients, periorbital swelling was mild and did not require any treatment. Periorbital swelling generally lasted between 6 and 30 days, however in one patient it was reported 2 times. The first time it lasted only a few days and the second time it lasted for almost 4 months. We will exclude patients with an increased risk in developing edema, such as those with renal, hepatic, or cardiac dysfunction. Furthermore, the development of swelling will be followed throughout the study by regular physical examination and serial body weight measurements.

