Similar effects on bone biomarkers were described for two compound classes that target bone resorption, albeit by different mechanisms, namely the bisphosphonates (BPs) and the RANKL-inhibitor (Receptor Activator of NF- κ B Ligand) denosumab (Prolia). Evidence obtained with antiresorptive treatments (BPs and RANKL-inhibitors) in children suggests that the suppression of osteoclast mediated bone resorption by 70% and more will lead to the appearance of radiographically visible transverse sclerotic bands (Glorieux et al 1998; Land et al 2006; Hoyer-Kuhn et al 2014). These bands may represent horizontal trabeculae formed during the temporary inhibition of epiphyseal activity (growth arrest lines) (Rauch et al 2014).

The width of the radiographically visible bands will depend on the duration of treatment and the growth velocity. Based on available evidence from the literature obtained with the RANKL inhibitor denosumab and various bisphosphonates, the effect should resolve after cessation of treatment (Wang et al 2014). The speed of this resolution will depend on two main factors: the thickness of the transverse sclerotic band and the degree of bone remodeling. Radiographic evidence disappears at approximately 4 years and 17 months after cessation of treatment for BPs and denosumab, respectively. This slow resolution is due to the long lasting antiresorptive effect of

BPs embedded on the bone surface, and the slow decrease of circulating antibody levels after stopping denosumab. Based on the difference in mechanism of action, it can be expected that the resolution of the bone effects will require less than 17 months when MCS110 treatment is stopped.

Confidential

Taken together, based on the known effects of antiresorptive agents on bone in children, it is likely that MCS110 can be administered without serious consequences to an adolescentpopulation for a limited amount of time such as 6 months, and that the effects should be fully reversible after withdrawal of the compound.

Corporate Confidential Information

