Tumor volumes will be listed and descriptively summarized at each MRI assessment time by treatment arm (treatment arm 1 = MCS110 3 mg/kg, treatment arm 2 = MCS110 5 mg/kg, treatment arm 3 = MCS110 10 mg/kg). For patients in treatment arms 1 and 2 that switch to 10 mg/kg after 3 doses, they will be treated as a separate group throughout the study (4= MCS110 3 mg/kg for 3 doses and 10 mg/kg afterwards and 5= MCS110 5 mg/kg for 3 doses and 10 mg/kg afterwards) This approach will be applied for all analyses of Part C where the treatment group is used. In addition, incidences of patients with partial response (PR), stable disease (SD) and progressive disease (PD) will be listed by treatment arm.

All summary tables (tumor volumes and response) will also be provided by age group (<18 years and ≥ 18 years).

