7.3.3.2 Analysis of mHAQ data - Parts B and C only

SF-36 has been replaced with mHAQ for part B as the team felt that SF-36 would not be evaluable due to the small number of patients in the study.

The modified Health assessment questionnaire (mHAQ) is a patient reported outcome (PRO) which is usually self-administered by the patient. The mHAQ is a modification of the HAQ. It was developed to include questions concerning perceived patient satisfaction regarding the same activities of daily living, along with perceived change in degree of difficulty. The number of activities of daily living was reduced from 20 (HAQ) to 8 (mHAQ).

The eight activities measured by the mHAQ are:

1. dressing and grooming
2. arising
3. eating
4. walking
5. hygiene
6. reach
7. grip
8. common daily activities

Patients are asked to rate these daily activities on a scale ranging from 1 to 4 with:

1. without difficulty
2. with some difficulty
3. with much difficulty

4. unable to do

The mHAQ is calculated as the average of the single scores. To do that the following scoring is applied:

- without difficulty = 0
- with some difficulty = 1
- with much difficulty = 2
- unable to do = 3

Values <0.3 are considered normal.

Summary statistics and graphical displays of overall mHAQ score will be provided. All mHAQ data will be listed by Part and treatment group.

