Data for Part B change from baseline of EQ5D_{vas} score at each visit will be plotted as an individual overlay plot with a mean (+/-SE) line overlaid.

Data for Part A, B and C pooled for weeks 1-4 change from baseline of EQ5D_{utility} score at Week 2 and 4 will be plotted as an individual overlay plot with a mean (+/-SE) line overlaid.

Data for Part B change from baseline of EQ5D_{utility} score at each visit will be plotted as an individual overlay plot with a mean (+/-SE) line overlaid.

Data for Part C change from baseline of EQ5D_{utility} score at each visit will be plotted as an individual overlay plot with a mean (+/-SE) line overlaid.

All data for EQ5D will be listed by Part and treatment group.

8 Statistical methods for safety and tolerability data

All safety data will be listed and summarized by Part unless otherwise stated.

Disposition

Frequency counts of the number of patients completing/discontinuing from the study will be provided together with frequency count of the reason for discontinuation

Demographics

A summary of demographics will be produced containing Frequency counts of Race, Ethnicity and Sex together with summary statistics for Baseline Age, Height, Weight and BMI, and other related baseline values.

Immunogenicity

All Anti-drug antibodies will be listed by treatment, patient, visit/time, antibody Y/N, titer value. Summary statistics will be provided by treatment and visit.

Vital signs

All vital signs data will be listed by treatment, patient, and visit/time and if ranges are available abnormalities (and relevant orthostatic changes) will be flagged. Summary statistics will be provided by treatment and visit/time.

In Part C all summary tables will also be provided by age group (<18 years and ≥18 years).

ECG evaluations

All ECG data will be listed by treatment, patient and visit/time, abnormalities will be flagged. Summary statistics will be provided by treatment and visit/time.

In Part C all summary tables will also be provided by age group (<18 years and ≥18 years).

Standard clinical laboratory evaluations

All laboratory data will be listed by treatment, patient, and visit/time and abnormalities will be flagged. Summary statistics will be provided by treatment and visit/time.

In Part C all summary tables will also be provided by age group (<18 years and ≥18 years).

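### As visible, the SAP groups exploratory DXA results by study Part only, so the planned Part C summary cannot show whether bone-density change differs by dose

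*SAP*

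**What the plan says.** SAP 7.3.3 covers DXA in Parts B and C and calls it exploratory. For tables and plots, "summary statistics and graphical displays for the change from baseline DXA will be provided by Part". For listings, "the data will be listed by Part showing the baseline, raw value and absolute change from baseline". A closing sentence repeats that all DXA data are listed by Part. Treatment group, dose, visit and age group are not mentioned.

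Other SAP rules on grouping are narrower than they may look:

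- **Treatment groups in Part C.** The Part C text of SAP 7.1 defines five groups: three dose arms, plus 3 mg/kg and 5 mg/kg patients who switch to 10 mg/kg. It then says "This approach will be applied for all analyses of Part C where the treatment group is used".
- **Age split, efficacy.** SAP 7.1: "All summary tables (tumor volumes and response) will also be provided by age group", with the scope limited in brackets to tumor volumes and response.
- **Age split, safety.** SAP section 8 states, under vital signs, ECG, standard laboratory and adverse events in turn, "In Part C all summary tables will also be provided by age group (<18 years and ≥18 years"). DXA is not one of those headings.
- **A neighbouring section.** SAP 7.3.3.2: "All mHAQ data will be listed by Part and treatment group".

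On bone risk, protocol 3.5.1 says "Changes in bone turnover and bone homeostasis will be closely monitored". Protocol 3.5.2 discusses extrapolation to the immature skeleton and, for sclerotic bands seen in children on other antiresorptive drugs, says "These bands may represent horizontal trabeculae formed during the temporary inhibition of epiphyseal activity (growth arrest lines").

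**The concern.** Part C randomises three starting doses. Protocol 3.2.3.2 gives its goal as a dose below 10 mg/kg that works as well and may have fewer side effects, and safety and tolerability are a primary objective (protocol 2.7). The protocol treats bone turnover and homeostasis as a risk of the drug. A bone-density summary is useful for that goal only if it can be read by dose.

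Followed as written, 7.3.3 gives one Part C summary over all doses and over patients whose dose changes at week 12. A change seen mainly at one dose would be diluted in that mean. If adolescents are scanned, the same mean would also combine growing and mature skeletons, while the SAP separates the two for other Part C safety tables.

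**Working it through.** The documents give no sample size, effect size, SD or error rate for DXA, so there is no stated figure to reproduce. The check is a reading of the grouping rules, followed by arithmetic on the planned counts.

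**1. Does another rule supply the missing grouping?**

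- The five-group rule applies where treatment group is used. Section 7.3.3 does not use it.
- The efficacy age split is bracketed to tumor volumes and response.
- The safety age split is repeated heading by heading, so it is not a general rule, and DXA is outside section 8.
- The mHAQ (7.3.3.2), EQ5D (7.3.3.3) and relapse (7.2.8) sections name Part and treatment group together. Section 7.3.3 says Part three times and adds nothing.

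No visible rule reaches DXA.

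**2. Which Part is affected?** Part B uses active drug at 10 mg/kg only (protocol 3.2.1), so no dose levels are pooled there. The dose problem is confined to Part C.

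**3. Dilution in the pooled Part C mean.** Planned starters are about 6, 6 and 3 on 3, 5 and 10 mg/kg (protocol Table 5-1), a total of 15. Extending one lower arm by about 4 gives 19. If an effect d is confined to the 10 mg/kg starters, the pooled mean shows d × (10 mg/kg starters) / (all patients):

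- no extension: 3/15 = 0.20 of d
- one arm extended: 3/19 = 0.16 of d

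For illustration, an assumed 5% loss in those three patients would appear as 0.2 × 5% = 1.0% in the pooled mean of 15.

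**4. After week 12.** Lower-arm patients with less than 45% tumor volume reduction move to 10 mg/kg if the drug is tolerated. If s of the 12 planned lower-arm patients switch, the share who have received 10 mg/kg is (3 + s)/15:

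- s = 0: 3/15 = 0.20
- s = 6: 9/15 = 0.60
- s = 12: 15/15 = 1.00

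The value of s is not known in advance, so 0.2 should not be carried beyond week 12. The visits at which DXA is done cannot be seen, because schedule rows are redacted.

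**5. What could a split show?** Assuming 80% power and two-sided 5%, the detectable difference in SD units is (1.96 + 0.84) × √(1/n1 + 1/n2). A noncentral-t calculation is given beside it.

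| Comparison | n | Normal | t |
|---|---|---|---|
| 10 vs 3 or 5 mg/kg | 3 vs 6 | 1.98 SD | 2.31 SD |
| 10 vs an extended arm | 3 vs 10 | 1.84 SD | 2.03 SD |
| 3 vs 5 mg/kg | 6 vs 6 | 1.62 SD | 1.80 SD |

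A split by dose would therefore be descriptive.

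**6. Age.** To size the effect of mixing ages one needs the number of adolescents with DXA and their expected change. The visible documents give neither, so no size is put on it.

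**The case against.** The strongest reply is that the sentence is loose rather than wrong. SAP 7.2.8 is headed as listed by Part, yet its body adds treatment group. Section 8 sets Part as the default and then breaks results down by treatment. Read that way, 7.3.3 means only a separate set of outputs for each Part. Redacted text (SAP before 7.3.3, protocol section 6.5.7 and parts of section 9) might also hold grouping rules. This stands as a caution, but in those other places the treatment breakdown is written out, and in 7.3.3 it is not. A programmer following the visible text would pool.

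It is also fair to say that DXA is exploratory and that CTX-I is collected as another bone measure, although it marks resorption rather than bone mass. A split would leave cells of 3 to 6 patients, fewer once switchers are separated. All of this limits the weight of the point. It does not favour pooling, since the SAP splits other descriptive Part C tables by treatment and age despite equally small numbers.

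Stronger readings are not supported:

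- **A reader might infer that a dose effect or harm to growing bone could not be seen at all.** The listings keep baseline, raw value and change for each patient. What is missing is a planned grouped summary.
- **A reader might infer that adolescents and adults are in fact mixed.** Section 7.3.3 sets no age limit, but no visible text shows that anyone under 18 has DXA.
- **A reader might infer that growth would hide a deficit of a stated size.** That needs growth rates and adolescent numbers that the documents do not give. The protocol's paediatric concern is also a radiographic finding, not a density loss.
- **A reader might infer that the summary uses raw change only.** Absolute change is specified for the listing; the summary sentence says only change from baseline.

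**Conclusion.** The point holds as a gap in the grouping rule for Part C. On the visible text, DXA summaries, plots and listings are by Part only, which pools three starting doses and the switchers, and the planned summary cannot show whether bone-density change differs by dose. An effect confined to the 10 mg/kg starters would appear at about 0.2 of its size until week 12 (0.16 with an extended arm). This assumes the planned 6, 6 and 3 allocation and a simple mean over patients. After week 12 the share depends on how many patients switch.

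The age part is conditional on adolescents having DXA and is not sized. Part B is not affected by dose pooling. No data are lost, no primary or secondary result changes, and the outcome is exploratory. I rate this a free improvement.

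**What to change.** In SAP 7.3.3:

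- Replace the by-Part grouping of summaries and plots with Part, treatment group and visit, pointing to the five groups in the Part C text of 7.1.
- Add treatment group to the DXA listing.
- If any patients under 18 have DXA, present the Part C summaries for under 18 and for 18 and over, as the other safety tables already do.
- Optionally, for adolescents, add an age- and sex-referenced score, but only where reference data for the scanner and site are available. Keep the raw change as well.

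The cost is a few words in the SAP and some extra table rows. No new data are needed, and no dose or clinical rule is touched. The drawback is very small cells, particularly for switchers and adolescents, so the tables should be labelled descriptive and read with the listing.
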